6.3 Description and rationale for conducting the trial

At present, there is minor evidence of using the phytoengineering-based drug product Imupret® in acute tonsillitis, pharyngitis and tonsillopharyngitis. The spectrum of its pharmacological properties includes antiviral, anti-inflammatory, and immunomodulatory action. The aggregate of these properties allows affecting almost all pathogenetic process links underlying the nosology in question, and favourable safety profile allows viewing Imupret as a basic therapeutic agent in treatment of non-bacterial forms of acute tonsillitis, pharyngitis, and tonsillopharyngitis. Our previous work showed that the use of Imupret in patients with non-bacterial tonsillitis accelerates regression of symptoms of tonsillitis and reduces the need for antibiotics. At the same time, there is a lack of studies, valid from the viewpoint of compliance with GCP standards have been conducted. Confirmation of high efficacy of Imupret in treatment of the above nosology group would be served as a justification for optimization of this nosology treatment scheme of delayed antibiotic prescription and recommendations for inclusion of this drug product into the national guidelines.

In the context of this clinical trial the two questions that are to be answered are:

1. Does Imupret®, taken during the diseases acute period help reduce the frequency of antibiotic use in children aged 6-12 ?
2. Does Imupret®, taken during the diseases acute period helps to accelerate the regression of symptoms in children aged 6-12?
3. Is the use of antibiotic delay technology safe for children aged 6-12 years?

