	Mode of administration and dosage regimen	
Imupret® oral drops
 
Dosage for acute symptoms:
 
Children from 6 to 12 years: 15 drops 5-6 times daily
 
Adults and adolescents from the age of 12 years: 25 drops 5-6 times daily
 
Dosage after acute symptoms have subsided:
 
Children from 6 to 12 years: 15 drops 3 times daily
 
Adults and adolescents from the age of 12 years: 25 drops 3 times daily

Duration of treatment	
Disease will be evaluated 36-48 hours prior to active treatment.
 
Active Imupret® treatment group: 10 treatment days
 
Reference treatment group: 10 days
 
Afterwards, there will be a follow up observation phase of 1 months
	

SCHEDULE OF ASSESSMENTS

V1		V2		V3 (Telephone call)					V4	V5
day 1	day 2	day 3	day 4	day 5	day 6	day 7	day 8	day 9	day 10	day 28

Study group 1

Imupret (dosage acute phase)
Reference treatment

Study group 2

Reference treatment

V1	day 1	Screening, randomization, prescription of treatment
V2	day 3	Status evaluation, possible prescription of antibiotics
V3	day 5 ±1	Evaluation of treatment efficacy, telephone call
V4	day 10 ±1	Evaluation of treatment efficacy, end of reference treatment
V5	day 28	Telephone call

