8 TRIAL PLAN

8.1 Trial design

This is an open-label, exploratory, comparative, multicenter, randomized, prospective, parallel-group phase IV clinical trial. The trial is designed in order to reveal effects of an additional Imupret therapy in comparison to the standard therapy alone (diet, NSAID, elimination of irritative factors, local anaesthetics).

Imupret® oral solution is registered and marketed in the Ukraine. The dose of Imupret was selected based on the recommendations given in the respective Summary of Product Characteristics of both dosage forms, which is also reflected in the package leaflet, respectively.

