8.3.3 Reference treatment

All patients of the trial will undergo the reference treatment described below. However, only one of the two study groups (study group 1) will receive and add-on treatment with either Imupret® oral solution (see 0 and 8.3.2).

Reference treatment comprises instructions for patient's behavior as well as possible medical treatment when needed:

- Sparing diet with fractional feeding (5-6 times a day) in only small portions explicitly excluding coarse, spicy, or heavily digestible food
- At the discretion of the investigator, elimination of all factors irritating pharyngeal mucosa (e.g. thermal, chemical influence etc.)

At the discretion of the investigator, Paracetamol as single doses up to 500 mg – not more than 3-4 times daily

- At the discretion of the investigator, topical treatment like benzydamine, lidocaine (in case of severe sore throat)
- At the discretion of the investigator, antibiotic treatment in case it is indicated with e.g. amoxicillin clavulanate, cephalosporins (in case of prescription of antibiotics patients will be evaluated separately)

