8.5 Time schedule and visits

Four scheduled visits will be performed during the first phase of the study:

First study phase

- 1 visit (1st day): screening, randomization and treatment; evaluation by Mc Isaac Score scale; LTM Scale (Local Tonsillitis Manifestation Scale): (5 symptoms: Sore throat at swallowing (0 – absent, 1 – mild, 2 – moderate, 3 – severe / pronounced); Sore throat at rest; Throat irritation at rest; Palatine tonsils hyperemia; Palatine tonsils edema); Patients self-assessment (VAS; 0-10)

- 2 visit (3rd±1 day): intermediate evaluation of the effectiveness of treatment - clarification of the patient's condition, the need to prescribe an antibiotic; evaluation by LTM Scale, patients self-assessment (VAS; 0-10)
- 3 visit: intermediate evaluation of the effectiveness of treatment (day 5-day ±1) via telephone (or visit if necessary); patients self-assessment (VAS; 0-10)
- 4 visit: final (10th day ±1 day). Evaluation by LTM Scale (0-15), patients self-assessment (VAS; 0-10)
- 5 Follow up; day 28: evaluation of the long-term effects of treatment
- - An unscheduled visit can be made if the patient's condition worsens (according to the patient and / or the researcher, including if the symptoms of the disease persist or worsen, including but not limited to an increase in the temperature in the armpit above 38.0 ° C at the 3rd and / or subsequent days of treatment).
- The total duration of the treatment: 10 days
- The total duration of the study for one patient is not longer than 38 days.

Any unscheduled visit may be carried out in case of worsening of the patient's condition (at patient's and/or investigator's opinion), including persistence or aggravation of the disease symptoms.

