9.3 Exclusion criteria

- Score -1 to 3 according to Mclsaac Scale.
- Indication for hospitalization, including:
 - o purulent complications (peritonsillar abscess and others);
 - o severe general condition.
- Indication for immediate initiation of systemic antibiotic therapy
- patients at risk of developing severe complications, including e.g. clinically relevant concomitant diseases of heart, lungs, kidneys, liver, neuromuscular apparatus, cancer diseases, immunosuppression, diabetes mellitus, cystic fibrosis.
- suspected infectious mononucleosis (by clinical signs);
- use of systemic antibacterial or antifungal agents, systemic glucocorticosteroids, cytostatics, immunomodulatory drugs, "interferons" or interferon derivatives during the last 14 days prior to inclusion;
- presence of haemorrhagic or pronounced necrotic process in oral cavity or pharynx, including the lymphoid ring.
- Intolerability or individual hypersensitivity to any of the study drug ingredients and the reference treatment scheme.

Patients who refuse to sign the informed consent or who do not agree to passing on of their pseudonymous data to the monitor / CRO, the sponsor, and competent national or European community authorities must not be included in this trial.

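### Question 3 asks whether delaying antibiotics is safe, but no arm is assigned immediate antibiotics and complications under delay are not securely recorded, so the trial can at most describe them

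*Protocol*

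**What the plan says.** Protocol section 6.3 opens its list with "In the context of this clinical trial the two questions that are to be answered are" and then gives three. The third is "Is the use of antibiotic delay technology safe for children aged 6-12 years".

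The rest of the plan bears on that question as follows.

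- **Randomised contrast.** Section 8.1 sets out to show "effects of an additional Imupret therapy in comparison to the standard therapy alone". The three objectives in section 7 (need for antibiotics, symptom regression, duration of antipyretic use) are all comparisons of Imupret with control.
- **Background care.** Section 8.3.3 says "All patients of the trial will undergo the reference treatment described below". That treatment includes "At the discretion of the investigator, antibiotic treatment in case it is indicated".
- **Timing of the antibiotic decision.** The synopsis has one visit schedule for both groups and places "Status evaluation, possible prescription of antibiotics" at visit 2, day 3. Sections 8.5 and 10.2 agree.
- **Population.** Section 9.2 requires severe acute tonsillitis with a McIsaac score of 4-5. Section 9.3 excludes "Indication for immediate initiation of systemic antibiotic therapy", purulent complications, and children at risk of severe complications.
- **Follow-up.** Section 8.5 describes day 28 as "evaluation of the long-term effects of treatment". Section 10.5 makes it a telephone call that checks well-being (AEs), restrictions and medication.
- **Safety analysis.** Section 12.2.4 and the SAP plan descriptive AE tables only. The AE definition in section 11.1.1 says that worsening of common symptoms, and other outcomes to be expected from the disease, are as a rule not recorded as AEs.

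**The concern.** A statement that delay is safe is normally heard as a statement about delay against treating at once. This trial randomises nobody to treatment at once, so no comparison between its arms bears on delay. The main harm to look for when antibiotics are withheld is a complication of the tonsillitis itself, and that is the kind of event the AE definition tends to leave out.

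Section 6.3 wants the results to support a delayed-prescription scheme and the drug's inclusion in national guidelines. An answer to question 3 would therefore be used outside the trial. Under the plan as written, that answer would come from uncontrolled AE tables in which the relevant events may be missing. A low count could then reflect how events were recorded rather than how often they occurred.

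**Working it through.** **1. The plan's own figure.** No sample size or precision is stated for question 3. The only calculation, in the synopsis, is for treatment response. With the tabulated z-values 1.96 and 0.84, response rates 0.75 and 0.90, e = 0.0 and d = 0.15, the printed formula gives

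(1.96 + 0.84)² / (0.0 − 0.15)² × [0.75 × 0.25 + 0.90 × 0.10] = 7.84 / 0.0225 × 0.2775 = 96.7, so 97 per group.

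Reading the dropout figure of 3 as a percentage, 97 / 0.97 = 100. The figure reproduces, but it sizes Imupret against control for efficacy and says nothing about delay.

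**2. Is there a contrast for delay?** Sections 7 and 8.1 make Imupret the only difference between the arms. Section 8.3.3 alone does not show that both arms follow a delayed strategy, because it gives no interval. Section 6.1 counts the 36-48 hours from the start of Imupret, which on its own would cover one arm. It is the common visit 2 decision (synopsis schedule, sections 8.5 and 10.2) that applies the waiting period to both groups. On either reading, no arm is assigned immediate antibiotics and no external control is named. The planned allocation for delayed versus immediate is 200 versus 0, so the difference cannot be estimated at any sample size.

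**3. Is a description of delay secured?**

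- Objective: none in section 7.
- Endpoint: sections 12.2.2 and 12.2.3 and the SAP list symptom scores, need for antibacterial therapy, temperature and self-assessments. Antibiotic need is counted per arm as an efficacy measure. No complication endpoint is defined.
- Analysis: AE frequencies only, with no acceptable rate to judge them against.
- Recording: section 11.1.1 generally leaves expected disease outcomes out of AEs. Section 11.1.2 defines an SAE as a kind of AE, so a hospital admission for such an outcome could be left out too.
- Control arm: section 11.1.1 defines an AE in a subject who has received the investigational product, which control children do not receive. Section 11.2 collects AEs from consent to the end of the trial. The two passages leave control-arm recording ambiguous.

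**4. What a perfect result would show.** With zero events in n children, the two-sided exact (Clopper-Pearson) 95% upper limit is 1 − 0.025^(1/n).

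| Children | n | Upper limit |
|---|---|---|
| Both arms pooled | 200 | 1.83% |
| One arm | 100 | 3.62% |
| Pooled, 97 per group | 194 | 1.88% |
| One arm, 97 | 97 | 3.73% |

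One-sided 95% limits, 1 − 0.05^(1/n), are 1.5% for 200 and 3.0% for 100.

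**5. Would an added arm be practical?** The documents give no complication rate or margin, so both are assumed here. Non-inferiority to an immediate-antibiotic arm (one-sided 0.025, 80% power, equal true rates) needs n = (1.96 + 0.84)² × 2p(1 − p) / margin² per arm, computed with unrounded z-values:

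| Assumed rate | Assumed margin | n per arm |
|---|---|---|
| 0.5% | 2 points | 196 |
| 1% | 2 points | 389 |
| 1% | 1 point | 1,555 |
| 2% | 1 point | 3,077 |

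On these assumptions, an added arm would generally mean a different and larger trial.

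**The case against.** The strongest reply is that question 3 never says compared with immediate antibiotics. It can be read descriptively, and describing events under one strategy needs no comparator. The trial also calls itself exploratory, and neither document plans a delayed-versus-immediate analysis. This stands in part: the question is not unanswerable in every sense. It does not remove the point, because the descriptive reading has no objective, endpoint or analysis behind it either.

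A second reply is that much of the information is already collected. Section 10.2 records antibiotic intake in the CRF, section 10.5 checks medication and AEs at day 28, section 11.1.2 makes inpatient admission a seriousness criterion, and section 8.5 allows an unscheduled visit for worsening. This also stands, and a reader should not infer that follow-up is blank. The gap is narrower: complications of the disease are not named anywhere as something to collect, and section 11.1.1 points towards leaving them out.

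A third reply is that patients given antibiotics will be evaluated separately (sections 8.3.3 and 10.2). That does not help. The group is formed after randomisation, by indication, and its members were also managed with the visit 2 decision.

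A reader might also infer that the children are simply low-risk. The documents do not support that. Those at risk of severe complications are excluded, but entry requires severe disease in the highest McIsaac band, to which the synopsis attaches a streptococcal probability of about 50%.

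**Conclusion.** The point holds as a mismatch between a stated safety question and what the trial can deliver. The trial cannot conclude that delay is as safe as immediate treatment. It could describe complication rates under delay in the selected population of sections 9.2 and 9.3, but the plan does not secure that description. With no events at all, an upper limit of 1.8% pooled or 3.6% in one arm is the best attainable. This assumes that every child is followed to day 28 and every complication is recorded. Whether 1.8% is reassuring cannot be judged, since the documents state no acceptable rate.

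It would be too strong to infer that the trial can say nothing about delay, or that the Imupret comparison is damaged by this point. The first overlooks the descriptive reading. The second is unsupported, because the randomised contrast in section 8.1 does not depend on question 3.

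**What to change.** - **Reword question 3** as a descriptive aim: the incidence of tonsillitis complications, hospital admission and later antibiotic use to day 28 under delayed prescription, pooled and by arm, with exact 95% confidence intervals.
- **Align the documents.** Correct the announced number of questions in section 6.3, add the aim to section 7, and add the endpoint and analysis to section 12.2 and the SAP. Say which events count as complications, and name the denominator, because neither document defines a safety set.
- **State the limit.** Add that no conclusion on delayed versus immediate antibiotics will be drawn.
- **Secure the recording.** State that these complications are recorded in both arms despite the exclusion in section 11.1.1, and ask about them by name at the visit 5 call.

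No new arm, visit or patient is needed. The cost is a more modest claim, some text changes, and a few extra questions in a call that is already scheduled.

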6.4 Risk / benefit assessment

Imupret combines the anti-microbial, anti-inflammatory and immune-modulatory effects of seven herbal drugs used traditionally in the combination product Imupret. Clinical surveys have demonstrated that it can be successfully applied in therapy of acute infections and inflammations of the upper respiratory tract.

The benefit of therapy with Imupret N can be concluded from long years of successful application in medical practice and in self-medication, but also from the results of the post marketing surveillances and experience report. Side effects observed in clinical surveys are almost exclusively gastro-intestinal complaints or allergic skin reactions which lead to intake termination or dose adjustment.

6.5 Guidelines for the development of the trial protocol

The moral, ethical, and scientific principles governing clinical research as set out in the Declaration of Helsinki from 2013, the principles of GCP as described in the ICH E6 guideline and the provisions of the EU Directive 2001/20/EC on the implementation of GCP in the conduct of clinical trials. All aspects of these regulations were observed in the clinical trial development process.

7 TRIAL OBJECTIVES

The aims of this clinical trial are:

To investigate the influence of Imupret prescriptions in the therapeutic concept of delayed prescription of antibiotics to:

- To compare the need for antibiotics in patients, received Imupret in addition to conventional therapy and in patients of the control group (received conventional therapy only)
- To evaluate the effect of the study drug in complex with conventional therapy versus conventional therapy only on regression of the tonsillitis symptoms
- To evaluate the effect of the study drug in complex with conventional therapy versus conventional therapy only on duration of antipyretic (paracetamol as antipyretic) administration.

8 TRIAL PLAN

8.1 Trial design

This is an open-label, exploratory, comparative, multicenter, randomized, prospective, parallel-group phase IV clinical trial. The trial is designed in order to reveal effects of an additional Imupret therapy in comparison to the standard therapy alone (diet, NSAID, elimination of irritative factors, local anaesthetics).

Imupret® oral solution is registered and marketed in the Ukraine. The dose of Imupret was selected based on the recommendations given in the respective Summary of Product Characteristics of both dosage forms, which is also reflected in the package leaflet, respectively.

8.2 Sample size estimation

The clinical trial is designed in order to obtain a valid description of the in vivo performance of the active (add-on) treatment of Imupret in comparison to the reference standard treatment alone. Endpoints are defined as exploratory endpoints. Depending of the data finally obtained, several exploratory descriptive and statistic evaluations will be performed, so that a biometricaly based sample size estimation is not necessary. However, in order to guarantee a sufficient sample size for exploratory analyses of the data captured, a sample size of N=200 will be included. Treatments will be assorted in a 1:1 ratio, i.e. N=100 will receive an add-on treatment with Imupret® and N=100 will receive the standard treatment only.

8.3 Trial treatment

The IMPs in this trial are Imupret® oral drops. The preparation is registered and available on the Ukrainian market without prescription. Therefore, the formulation, manufacturing, packaging and labelling of the IMPs follow the principles of Good Manufacturing Practice and currently valid national Ukrainian requirements. The detailed description covering all aspects regarding quality and safety of Imupret® oral drops are part of the respective Summary of Product characteristics.

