It should be noted that unjustified antibiotic therapy of acute tonsillitis is only based on the symptom "sore throat" or "exudate (plaque) tonsils" and plays a significant role in the formation of antibiotic resistance. Antibiotic therapy does not affect pain. In order to avoid the

irrational use of antibiotics, one should distinguish the desire of the patient or his parents to get rid of the pain, from the rational assessment of the doctor for all pros and cons about an antibacterial therapy.

To prevent unjustified prescription of antibiotics, a therapeutic concept of delayed administration is proposed. A patient with acute tonsillitis is prescribed treatment with antibacterial agents in a delayed manner (a prescription is written out, the dose and the frequency of administration is calculated). In the absence of positive effect within 36-48 hours from the beginning of treatment with Imupret the antibacterial therapy with antibiotics is started. The advantage of deferred antibiotic prescription is, that a higher number of patients and doctors, awaiting antibiotic therapy, may be more agreeable with this way of treatment than with a complete rejection of the antibiotics prescription. This is why delayed use of antibiotics is an important treatment strategy to reduce the number of unreasonable prescription of antibacterial agents.

Considering this fact, it becomes necessary to use drugs with a complex effect on the main processes of pathogenesis and have an evidence-based efficacy base for acute tonsillitis. At the present moment, there is an insignificant evidence base for the application of the phytonoering drug Imupret in acute tonsillitis. The spectrum of its pharmacological properties includes antiviral, antibacterial, antiinflammatory and immunomodulating effects. The combination of these properties makes it possible to influence practically all parts of acute tonsillitis. Additionally a good safety profile allows to consider Imupret as an adequate basic therapy for the treatment of acute tonsillitis, especially in the therapeutic concept of of delayed prescription of antibiotics. The already existing studies were not conducted under GCP conditions. Confirmation of the high effectiveness of Imupret in the treatment of acute tonsillitis would serve as a rationale for optimizing the treatment regimen of this nosology and recommendations for the inclusion of the drug in national guidelines.

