8.3.4 Concomitant medication not allowed

Patients need to be withdrawn from the study in case of the administration of the following medication groups:

- Inhaled and systemic corticosteroids
- Interferon preparations
- Antiviral drugs
- Immunomodulators
- Antihistamines

Patients may be withdrawn following the intake of any medication which, at the discretion of the investigator, might interfere with the objectives of the trial.

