8.4 Randomization

The clinical part of the trial will be open and randomized with no blinding procedure. Subjects will be randomly assigned to one of the two possible treatments with according to the underlying randomization list. Randomization will be performed using [StatSoft – generator of random figures] software.

The appropriate number of the randomisation schedule and associated treatment will be allocated for each subject whose entry in the randomised part of the clinical trial is confirmed. The randomisation list will be part of the trial documentation.

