9.2 Inclusion criteria

- Children (males/females), 6 - 12 years old, with severe acute tonsillitis.
- Possibility to initiate therapy within 72 hours since the onset of the disease symptoms.
- Score 4-5 according to Mclsaac Scale.
- Patient's and (or) one of his/her parents' willingness and ability to fulfil the requirements of the Study Protocol.
- Signed informed consent of the patient and (or) his/her parents for participation in the study.

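### Over-the-counter Imupret is not named in the exclusion or prohibited-medication rules, and the status of a control who takes it is left open

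*Protocol*

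**What the plan says.** **The contrast.** All patients receive reference treatment, and "only one of the two study groups (study group 1) will receive and add-on treatment" with Imupret (Protocol 8.3.3). Section 8.2 gives the other 100 patients standard treatment alone. There is no masking: "The clinical part of the trial will be open and randomized with no blinding procedure" (8.4).

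**Access to the drug.** Section 8.3 states: "The preparation is registered and available on the Ukrainian market without prescription". Section 8.3.2 gives tonsillitis as an indication, and section 6.4 counts self-medication among the established uses. One entry condition is "Possibility to initiate therapy within 72 hours since the onset of the disease symptoms" (9.2), so a child may have been ill at home for up to three days before Visit 1.

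**Medication rules.** Section 8.3.4 begins "Patients need to be withdrawn from the study in case of the administration of the following medication groups" and lists inhaled and systemic corticosteroids, interferons, antivirals, immunomodulators and antihistamines. A residual clause follows: "Patients may be withdrawn following the intake of any medication which, at the discretion of the investigator, might interfere with the objectives of the trial". Section 9.3 excludes several drug classes, immunomodulatory drugs among them, if used in the 14 days before inclusion. Neither section names Imupret or Tonsilgon, its former name (6.2.1.2).

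**How the protocol describes Imupret.** Section 6.1: "The spectrum of its pharmacological properties includes antiviral, antibacterial, antiinflammatory and immunomodulating effects". Section 6.3 again calls it antiviral and immunomodulatory.

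**Analysis sets.** Under Protocol 12.2.1 and the SAP, the FAS requires a recorded dose of IMP and one post-baseline observation. The PPS removes major deviations, which are not listed and are judged at data review.

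**The concern.** In an open trial of a product that families can buy, and that is labelled for the child's illness, use in the control arm is foreseeable. The plan should settle three things: whether such use is allowed, how it is detected, and how the patient is analysed. None is settled clearly for non-study Imupret.

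If controls who take it stay in, the arms become more alike and the differences in symptoms and antibiotic need shrink. If they are withdrawn, the control arm loses patients after randomisation, possibly those whose families were unhappy with progress. If sites choose differently, the control arm mixes both. Use before Visit 1 raises a related problem, because the baseline of a child in either arm may already be an on-drug value.

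**Working it through.** **1. Do the class terms cover Imupret?** Set 8.3.4 and 9.3 beside 6.1, 6.3 and 8.3.3.

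- *If they do*, a control who takes Imupret must be withdrawn, and a child given it in the previous 14 days is ineligible. But 8.3.4 applies to all patients and makes no exception for the allocated product, so every patient in study group 1 would also have to be withdrawn. That cannot be intended.
- *If they do not*, only discretionary wording is left: the residual clause of 8.3.4, and the withdrawal reasons in 9.4.1 for non-adherence and poor compliance. These permit withdrawal. They do not say that the use is recorded as a deviation and the patient followed and analysed as randomised. Withdrawn patients are not replaced (9.4.2).

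Two sites could reach opposite answers from the same text.

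**2. Is use recorded?**

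| Contact | Medication item in Protocol 10.1–10.5 | Imupret named for non-study use? |
|---|---|---|
| V1 | Prior and concomitant medication, to file and CRF | No |
| V2 | Medication check | No |
| V3 (call, day 5 ±1) | None listed | No |
| V4 | Medication check | No |
| V5 (call, day 28) | Medication check | No |

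General recording therefore exists. The gaps are a named question and any medication item at V3.

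**3. How is a control user classified?** PPS status is left to data review. For the FAS, section 8.3 identifies the IMP as Imupret drops. Read literally, a control enters the FAS only if an Imupret dose is documented, so crossover is what would admit that control. The intention is surely otherwise, but the wording needs repair before any rule about crossover can work.

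**4. Size: illustration only.** Inputs from synopsis Table 1: control rate 0.75, Imupret rate 0.90, z-values 1.96 and 0.84, 97 per arm.

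Plan's own figure: Table 1 enters 0.0 for e and 0.15 for d, so the squared term is 0.0225, as in an ordinary test of a 15-point difference.

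n = (1.96 + 0.84)² / 0.0225 × (0.75 × 0.25 + 0.90 × 0.10) = 7.84 / 0.0225 × 0.2775 = 96.7, rounded up to **97**. Adding 3 for dropout gives 100. Both figures reproduce.

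Now let a share c of controls take Imupret with its full effect. The documents give no value for c, so it is assumed.

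- Control rate: p = 0.75 + 0.15c
- Power = Φ( (0.90 − p) / √{[p(1 − p) + 0.09] / 97} − 1.96 )
- Example, c = 0.10: p = 0.765; standard error = √(0.269775 / 97) = 0.0527; 0.135 / 0.0527 − 1.96 = 0.60; power 72.6%.

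| c | Control rate | Difference (points) | Power, 97 per arm | n per arm for 80% |
|---|---|---|---|---|
| 0% | 75.0% | 15.0 | 80.1% | 97 |
| 5% | 75.75% | 14.25 | 76.5% | 106 |
| 10% | 76.5% | 13.5 | 72.6% | 117 |
| 20% | 78.0% | 12.0 | 63.7% | 143 |
| 30% | 79.5% | 10.5 | 53.8% | 181 |

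The last column uses unrounded z-values. The pooled formula gives power about one point lower in each row.

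**5. Direction if users are withdrawn.** Take c = 10% of 100 controls.

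- Counted as not effective, when they would otherwise have responded at 75%: 0.9 × 75% = 67.5%, a difference of 22.5 points.
- Dropped from the analysis, at the extreme where all 10 would have failed: 75 / 90 = 83.3%, a difference of 6.7 points.

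The sign of the bias around 15 points depends on a counting rule that the plan does not give.

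**The case against.** A reader might infer that nothing bars or records non-study Imupret, that a control can take it and still count as compliant, and that the damage could never be recovered. The documents do not support any of these.

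- **Recording.** V1 takes a medication history, V2, V4 and V5 check medication, and section 12.1 provides for dictionary coding of medication and listing of all clinical data.
- **Barring.** The 14-day exclusion and the listed classes may apply. Sections 8.2 and 8.3.3 confine Imupret to study group 1, so a control who takes it departs from allocation, and 9.4.1 permits withdrawal for non-adherence.
- **Compliance.** PPS status is undecided, which is different from compliant.
- **Recovery.** Section 9.4.1 requires the date and reason of each withdrawal, so use and withdrawals could be tabulated by arm, though less reliably without a named question.
- **Unseen material.** Consent pages are not in the public documents and may instruct controls. The visit checks on restrictions suggest that some instructions are given.

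The size is also open to challenge. The crossover shares are assumed, and full effect in a late or irregular user is generous. The calculation uses an ordinary difference test, although the synopsis words its hypothesis around a 15% margin. Sections 8.2 and 12.2 disclaim a formal sample size. Retained crossover pulls towards no difference and would not by itself create a false positive.

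All of this stands and limits the point. It does not resolve the conflict over the class terms, supply a named question or a V3 medication item, or say how a control user is analysed.

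**Conclusion.** The point holds as a gap in definition. Non-study Imupret is foreseeable in the control arm and before entry, but it is not named in 9.3 or 8.3.4. The class terms either leave it out or, taken literally, also capture study group 1. General recording exists but is not targeted, V3 has no medication item, and classification waits for data review in an open trial.

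The documents do not show how common such use would be. With full effect in users and the synopsis rates, 5% to 30% use would lower power from 80% to between about 77% and 54% and the expected difference from 15 to between 14.25 and 10.5 points. These figures apply only to the synopsis calculation. Dilution of the estimate would occur whether or not a formal test is run. If users are withdrawn instead, the direction of bias depends on how they are counted.

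**What to change.** 1. **Reconcile 8.3.4 and 9.3 with 6.1, 6.3 and 8.3.3.** State that the class terms do not refer to the allocated study product, that non-study Imupret or Tonsilgon taken for the current episode before V1 is an eligibility matter, and that study group 2 is not allocated it, so use there is a protocol deviation. The clinical handling of such a child is for the sponsor and investigators to settle.
2. **Ask by name.** At V1 to V5 in both arms, including the V3 call, ask about non-study Imupret or Tonsilgon and record days of use.
3. **Fix the analysis before data review.** Define control use as a major deviation, excluded from the PPS, with outcomes still collected and analysed in the FAS as randomised.
4. **Reword the FAS** in Protocol 12.2.1 and the SAP so that controls do not need a documented IMP dose.
5. **Report** non-study use by arm.

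The cost is a few sentences in the protocol and SAP, one added question at existing contacts, and perhaps a few more screen failures. No new visits are needed.
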